6.3 Safety Analysis Set

The Safety Analysis Set (SAS) includes all subjects who received a study injection. Subjects will be analyzed as treated for the SAS.

7. GENERAL ISSUES FOR STATISTICAL ANALYSIS

7.1 General Statistical Methodology

Unless otherwise specified, efficacy analyses will be performed on the FAS and PPAS; general safety analyses will be performed on the SAS. The number of evaluable subjects in any analysis set may vary by endpoint/timepoint based on missing data.

For continuous variables, the outcome measure at each visit, as well as the absolute change (outcome at visit – outcome at baseline), will be summarized within each treatment group using descriptive statistics (number of subjects, mean, SD, median, minimum, and maximum). Categorical variables will be summarized with counts and percentages.

Data collected from unscheduled visits will not be included in summary tables but will be included in subject-level listings as appropriate.

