7. STUDY PROCEDURES AND SCHEDULE

7.1 STUDY PROCEDURES/EVALUATIONS

7.1.1 STUDY SPECIFIC PROCEDURES

Collection of Adverse Events Data

Data regarding AEs will be collected in this study. AEs are events that occur during the study that are not present prior to Day 1 study medication injection, or, if present at the time of study medication injection, have worsened in severity during the study. AEs will be assessed at each in-person and phone visit from the time of study medication injection on Day 1 through Week 28 (EOS)/ET.

Each subject will be observed and queried by the Investigator or designee at each study visit for any continuing AEs or new AEs since the previous visit. The subject may be asked to return to the site for an unscheduled visit if an AE occurs between study visits, and if, in the opinion of the

Investigator, the AE requires a study visit for full evaluation. The following information will be recorded within the eCRF for each AE: Description of the event, date of onset and resolution, etiology, and severity as assessed by the Investigator according to the Clinical Data Interchange Standards Consortium (CDISC) Severity/Intensity Scale for Adverse Events (AESEV) ([Table 1](#)), causal relationship to study medication, outcome, and any action taken.

In this protocol, signs and symptoms of exacerbation or worsening of target knee OA will be captured in the context of efficacy assessments and recorded on specific pages of the eCRF or electronic diary. Anticipated fluctuations or anticipated deterioration (in the opinion of the Investigator) of the underlying disease (target knee OA) will not be considered as AEs nor captured on the AE page of the eCRF.

Whenever possible, it is preferable to record a diagnosis as the AE term rather than a series of symptoms relating to a diagnosis. Fluctuations of pre-existing conditions that do not represent a clinically significant exacerbation or worsening need not be considered AEs.

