7.2 LABORATORY PROCEDURES/EVALUATIONS

7.2.1 CLINICAL LABORATORY EVALUATIONS

Samples for clinical laboratory analysis by Medpace Central Laboratories will be collected by a qualified staff member at the Screening Visit and Weeks 4, 12, 24, and 28 (EOS)/ET. Refer to the Laboratory Manual for details about collection of specimens. At a minimum, the following tests will be conducted:

- **Chemistry panel:** Albumin, alkaline phosphatase (ALP), alanine aminotransferase (ALT), aspartate aminotransferase (AST), blood urea nitrogen, bicarbonate, calcium, calcium (corrected total), chloride, creatinine, glucose, lactate dehydrogenase (LDH), potassium, sodium, bilirubin (total)
- **Hematology:** Hemoglobin, hematocrit, red blood cell (RBC) count, white blood cell (WBC) count with differential, and platelet count
- **Urinalysis:** Clarity, specific gravity, pH, protein, glucose, ketones, nitrite, leukocyte esterase, and occult blood

An HbA1c test will be performed on all subjects at the Screening Visit.

Urine microscopy will be performed if urinalysis urine protein, leukocyte esterase (WBC esterase), occult blood, or nitrite values are out of range, or if the Investigator deems that the microscopy is clinically warranted.

The Investigator or designee must review the results of each subject's Screening Visit clinical laboratory test results prior to the Day 1 visit. The subject must not be randomized on Day 1 if any of the Screening Visit results are outside the normal range for the laboratory AND, in the opinion of the Investigator, are clinically significant.

The results of the clinical laboratory tests will be reported on the laboratory's standard reports. The Investigator must review all laboratory reports in a timely manner, noting "not clinically significant" (NCS) or comment on the clinical significance of any result that is outside the normal range for the laboratory, then date and initial the report. The Investigator must report all laboratory results that are BOTH outside the normal range for the laboratory AND, in the opinion of the Investigator, are clinically significant. If any abnormal, clinically significant laboratory measure is found prior to study medication injection, the subject is to be excluded. If it is found after study medication injection, it should be reported as an AE.

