7.1.1 Baseline

Baseline is defined as the last value recorded for any given parameter prior to study medication injection.

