10.2 Clinical Laboratory Evaluations

All chemistry, hematology and urinalysis results from the central laboratory will be summarized into shift tables as normal, non-clinically significant abnormal, and clinically significant abnormal. Assessments of clinical significance for abnormal values were made by the investigator on results that were outside of the normal range. Shift tables will compare the number and percent of assessments from each visit to baseline values for each treatment group.

All chemistry and hematology results from the central laboratory will be summarized for each treatment group. Descriptive statistics of each laboratory test at all timepoints will be provided along with the change from baseline at each subsequent visit. If a result is below the limit of quantification, it will be set to half the value for analysis (e.g., “< 3” will be analyzed as 1.5). The International System of Units (SI) will be used for all summaries.

Abnormal chemistry, hematology, urinalysis, and urine microscopy results for each subject will be provided in listings that will include laboratory test name, result, normal range, and an

explanation for clinically significant values. HbA1c values will be listed in conventional units (%).

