10.3 Vital Signs and Weight

Weight and vital signs (including systolic blood pressure, diastolic blood pressure, pulse rate, respiratory rate, and body temperature) will be summarized for each treatment group. Descriptive statistics of each parameter at baseline will be provided along with the change from baseline at each subsequent visit. A subject-level listing will also be provided.

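### Unscheduled laboratory and vital-sign values are kept out of the by-arm tables and no worst post-baseline summary is planned, so between-visit findings are compared by arm only if they are reported as AEs

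*SAP*

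**What the plan says.** The general rule is in SAP 7.1: "Data collected from unscheduled visits will not be included in summary tables". The same sentence sends these data to listings by subject, where appropriate.

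SAP 10.2 plans two kinds of laboratory table. For shifts, with the categories normal, abnormal but not clinically significant, and clinically significant abnormal: "Shift tables will compare the number and percent of assessments from each visit to baseline values for each treatment group". For chemistry and hematology values: "Descriptive statistics of each laboratory test at all timepoints will be provided along with the change from baseline at each subsequent visit". The section opens by committing all central-laboratory chemistry, hematology and urinalysis results to the shift tables, and it makes no exception for unscheduled ones. Abnormal results are also listed by subject.

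SAP 10.3 covers vital signs and weight: "Descriptive statistics of each parameter at baseline will be provided along with the change from baseline at each subsequent visit". It adds a subject-level listing. It plans no vital-sign shift table and defines no vital-sign categories.

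Protocol 7.2.1 schedules laboratory samples "at the Screening Visit and Weeks 4, 12, 24, and 28 (EOS)/ET". On visits outside the schedule, Protocol 7.1.1 says: "The subject may be asked to return to the site for an unscheduled visit if an AE occurs between study visits". The condition is that the Investigator thinks the event needs a visit for full evaluation.

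SAP 7.1.1 sets baseline: "Baseline is defined as the last value recorded for any given parameter prior to study medication injection".

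**The concern.** Laboratory measures and vital signs are part of the safety endpoint for the whole study (Protocol 3.2.3, SAP 3.2.3), alongside AEs and SAEs. Protocol 10.4.4 evaluates safety by AEs and also by changes in laboratory parameters and vital signs. The second of these is tabulated only at fixed visits.

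The excluded values are unlikely to be a random sample. The one reason the protocol gives for an unscheduled visit is an AE that needs evaluation, so values taken there may well be more often abnormal than those from routine visits. Leaving them out of by-visit means and shifts is sensible, because they would mix different times and reasons for sampling. The gap is that no other by-arm table takes them in. A reader of the safety tables could not see, for each arm, how many subjects ever reached an abnormal category or how extreme the values became.

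**Working it through.** The plan gives no figure to reproduce on this point, so the check is mainly one of text.

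**Where an unscheduled value goes.** Inputs: SAP 7.1, 10.1, 10.2 and 10.3; Protocol 7.1.1 (vital signs) and 7.2.1 (laboratory), both of which make a clinically significant abnormality found after injection an AE.

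| Value from an unscheduled visit | By-visit or shift table | AE tables by arm | Listing |
|---|---|---|---|
| Laboratory, out of range, clinically significant | No | Yes, as an AE term | Yes |
| Laboratory, out of range, not clinically significant | No | Not required | Yes |
| Vital sign, abnormal and clinically significant | No | Yes, as an AE term | Yes |
| Vital sign, any other | No | Not required | Yes |

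The second and fourth rows have no assured route to a by-arm table. In the first and third rows the event is counted, but its size is not tabulated, nor (for laboratory results) its shift category. The protocol prefers a diagnosis as the AE term, so the analyte and the direction of change may not be visible either.

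**Conflict within the SAP.** SAP 10.2 puts all central-laboratory results into shift tables; SAP 7.1 takes the unscheduled ones out of summary tables. If 7.1 governs, a clinically significant unscheduled result is an AE but is missing from the clinically significant column of the shift table, so the two displays can disagree.

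**Baseline.** The Schedule of Events has laboratory sampling at Screening and none on Day 1, so any repeat before injection would be unscheduled. SAP 7.1.1 would make that repeat the baseline. SAP 7.1 does not say whether its exclusion leaves this untouched.

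**How sparse the scheduled samples are (illustration only).** Post-baseline draws fall on nominal Days 29, 85, 169 and 197. The gaps from Day 1 are 29 − 1 = 28, 85 − 29 = 56, 169 − 85 = 84 and 197 − 169 = 28 days. Assume onset is uniform over Days 1 to 197, visits fall on nominal days, and an abnormality lasts L days; the documents give no value for L. For L up to 28 the onset days that catch each draw do not overlap, so the share meeting at least one draw is 4L/197:

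- L = 14: 56/197 = 28%
- L = 21: 84/197 = 43%
- L = 28: 112/197 = 57%

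These shares describe sampling sparseness. They do not measure the effect of the SAP 7.1 rule, which depends on how many unscheduled samples were taken, and the documents do not give that number.

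**The case against.** The strongest reply is that AE reporting already covers what matters. Clinically significant laboratory and vital-sign findings after injection must be reported as AEs whatever the visit type, and SAP 10.1 tabulates AEs by arm by system organ class, preferred term, severity, seriousness and relationship. This stands. A reader might infer that between-visit abnormalities are absent from the arm comparison altogether; the documents do not support that. What is lost is narrower: numeric values, shift categories, and results judged not clinically significant.

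A reader might also infer that the comparison between arms is biased. The documents do not show this. The rule is the same for both arms, assessors are meant to be blinded (SAP 4.3), and no formal safety tests are planned.

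The link between AEs and unscheduled visits is permissive: a subject may be asked back, and nothing requires laboratory samples or vital signs at such a visit. The number of values affected could be small. That limits the size of the point but does not close the gap.

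On baseline, a contradiction is tempting but too strong. SAP 7.1.1 is the specific definition, and the sentence in 7.1 concerns what tables display. One clarifying sentence is enough.

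Read literally, SAP 7.1 might also seem to drop AEs first recorded at an unscheduled visit. SAP 10.1 starts from all AEs collected, so that reading is not supported.

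**Conclusion.** The point holds as a minor gap in safety reporting. Under SAP 7.1, 10.2 and 10.3, unscheduled laboratory and vital-sign values enter no by-arm table of values or shifts, and no worst post-baseline summary makes up for it. They reach the by-arm displays only through Investigator judgment and AE reporting. SAP 7.1 and the opening of 10.2 also need to be reconciled.

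Its size cannot be stated, because it depends on an unknown number of unscheduled values. The conclusion rests on reading the shift tables as summary tables, which fits SAP 10.2, where results are described as being summarized into them. Efficacy conclusions are not affected.

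**What to change.** - Add by-arm shift tables from baseline to worst post-baseline category for chemistry, hematology and urinalysis, using scheduled and unscheduled central-laboratory results. The three categories in SAP 10.2 can be ordered as they stand, so no new limits are needed.
- Add by-arm summaries of maximum and minimum post-baseline vital signs on the same basis. A vital-sign shift table would first need categories, which the plan does not define.
- Keep the by-visit tables on scheduled data, and reword the opening of SAP 10.2 so that it agrees with 7.1.
- State in one sentence that the exclusion in SAP 7.1 does not alter the baseline definition in 7.1.1, so a repeat taken before injection can serve as baseline.

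The cost is a few more tables. They need no new data, and they may add little if unscheduled values turn out to be few.

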7.1.1 Baseline

Baseline is defined as the last value recorded for any given parameter prior to study medication injection.

7.1.2 Mixed-Effects Model for Repeated Measures

A mixed-effects model for repeated measures (MMRM) will be used to evaluate Pain NRS, WOMAC, and Patient Global Assessment outcome measures. The null hypothesis is that the mean difference in the endpoints between the two treatment groups is zero, versus the alternative hypothesis that this difference is not zero. The hypotheses can be expressed as follows:

$$H_0: (\beta_1 - \beta_0)_t = 0$$

$$H_A: (\beta_1 - \beta_0)_t \neq 0,$$

where β_0 refers to the least squares mean change from baseline in the placebo group and β_1 refers to the least squares mean change from baseline in the active treatment group, evaluated at timepoint t .

For Pain NRS, the model will be estimated assuming a Toeplitz variance-covariance matrix. The Toeplitz structure is a more generalized form of autoregressive-1 (AR1) structure, allowing the data to inform how the correlation between within-subject observations decreases over time instead of implicitly defining a uniform decay structure (Kincaid, 2005).

For WOMAC and Patient Global Assessment, the model will be estimated assuming an unstructured variance-covariance matrix, allowing the data to fully inform the correlation between within-subject observations (Kincaid, 2005).

MMRM presumes that missing data are not caused by something observable within the conduct of the trial (i.e. missing-at-random [MAR]). It is plausible to presume a MAR mechanism as there have been no observed tolerability issues to the administration of study injection during the prior development trials. Additionally, the study injection cannot be removed after it has been administered, eliminating study drug discontinuation as a source of treatment estimate confounding.

7.1.3 Analysis of Covariance

Analysis of Covariance (ANCOVA) will be used for continuous efficacy outcome measures to test the following hypotheses:

$$H_0: (\beta_1 - \beta_0) = 0$$

$$H_A: (\beta_1 - \beta_0) \neq 0$$

In the statement above, β is the least squares estimate in the change in the continuous efficacy outcome from baseline, where β_0 is the estimate for placebo and β_1 is the estimate for the active treatment group. The models will be adjusted for baseline value of the outcome.

7.1.4 Adjustment for Multiplicity

Familywise error rate will be controlled in the strong sense using the closed, fixed sequence testing method (Dmitrienko, Tamhane, & Bretz, 2010). All hypothesis tests will be evaluated in the sequential order described in [Section 9](#).

7.1.5 Data Handling for Patients Who Withdrew from the Study

If a subject discontinues the study, early termination assessments will be performed according to the protocol. If these assessments occur during a scheduled visit, they will be associated with that visit for the purposes of FAS analysis.

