4. STUDY DESIGN

4.1 DESCRIPTION OF THE STUDY DESIGN

This study is a multicenter, randomized, double-blind, placebo-controlled, parallel group study of a single dose of SM04690 injected into the target knee joint of moderately to severely symptomatic OA subjects at Day 1.

Approximately 726 subjects will be enrolled and randomized at a ratio of 1:1 (0.07 mg active per 2 mL injection: 2 mL Placebo). Subjects will participate in a 7- to 11-day screening period followed by a single injection and a 28-week evaluation period. Clinic visits will be scheduled at the Screening Visit, Day 1, and Weeks 4, 12, 24, and 28 (EOS)/ET. Phone visits will be scheduled at Weeks 8, 16, and 20. Specific timing of protocol procedures is described in the Schedule of Events Table ([Section 7.3.7](#)). Specific timing of electronic diary and questionnaire completion is described in the Schedule of Electronic Diary and Questionnaire Completion Table ([Section 7.3.8](#)).

This study will be conducted at approximately 100 investigational centers.

A Widespread Pain Index and Symptom Severity (WPI&SS) assessment will be administered at the Screening Visit and Day 1.

Subjects will be required to complete an electronic diary for the following ([Section 7.3.8](#)):

- Daily pain NRS from the Screening Visit through Week 28 (EOS)
- WOMAC at baseline and Weeks 4, 12, 24, and 28 (EOS)
- Patient Global Assessment at baseline and Weeks 4, 12, 24, and 28 (EOS)

In addition, general medical evaluations including physical examination, knee examination, and recording of vital signs will be performed at the Screening Visit, Day 1, and Weeks 4, 12, 24, and 28 (EOS)/ET. Height will be measured at the Screening Visit and weight will be measured at the Screening Visit and Weeks 28 (EOS)/ET. Clinical laboratory evaluations will be performed at the Screening Visit and Weeks 4, 12, 24, and 28 (EOS)/ET. Investigator assessment of NSAID/acetaminophen usage will be performed at all in-person and phone visits starting at Day 1.

Recording of signs and symptoms of study medication intolerance and AE reporting will start following the injection of the study medication and continue at all subsequent in-person and phone visits until the subject completes Week 28 (EOS)/ET. All AEs, whether volunteered, elicited, or noted during examination, will be recorded throughout the study.

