The WPI&SS assessment consists of a body map that determines a subject's areas of pain or tenderness (WPI) and symptom severity (SS) questions. The WPI&SS assessment used in this study is modified from that described in [\(Clauw 2014\)](#). A WPI&SS assessment will be

completed by the subject at the Screening Visit and Day 1.

Upon completion of the WPI&SS assessment, the subject will sign or initial the source document and date it to indicate that the assessment is reported accurately.

The WPI&SS assessment sheets will be provided by the Sponsor and may not be reproduced.

Electronic Diary Device Provision and Training

Detailed instructions and site training regarding subject electronic questionnaire completion will be provided to the investigational center. Electronic diary device provisioning to the subject will occur at the Screening Visit and electronic diary devices are to be returned to the site at Week 28 (EOS)/ET.

Subject training for electronic diary and questionnaire completion on the electronic diary device is required at the Screening Visit prior to subject completion of the pain NRS, WOMAC, and Patient Global Assessment questionnaires. Training will remain available on the electronic diary device throughout the study in case subject retraining is needed.

Additionally, at the Screening Visit, subjects will have training on accurate pain reporting and placebo response reduction prior to subject completion of the pain NRS, WOMAC, and Patient Global Assessment questionnaires. It is recommended that subjects complete the training on accurate pain reporting and placebo response reduction at Day 1 and Weeks 4, 12, and 24.

Pain Numeric Rating Scale

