7.3.6 EARLY TERMINATION VISIT

If possible, the following procedures and assessments should be performed within 14 days of subject premature withdrawal or termination.

- Collection of AE and concomitant procedures/therapies/medication data

Protocol SM04690-OA-10

Samumed, LLC

AM03V00

12 May 2020

- Review of medical history
- Assessment of NSAID/acetaminophen usage
- Physical examination, including knee examination of both knees
- Weight measurement
- Vital sign measurements (pulse rate, blood pressure, respiratory rate, and temperature)
- Venipuncture and collection of samples for clinical laboratory tests

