7.3.8 SCHEDULE OF ELECTRONIC DIARY AND QUESTIONNAIRE COMPLETION TABLE

	WOMAC and Patient Global Assessment	Daily pain NRS
Study Week/Day	WOMAC and Patient Global Assessment will be completed by subjects 5 days after the Screening Visit (or up until the day before the Day 1 visit), at Week 4 (with a window of \pm 3 days), and at Weeks 12, 24, and 28 (with a window of \pm 7 days) in the evening (between 5:00 pm and 11:59 pm local time) remotely on their electronic devices, as outlined below; ranges shown are inclusive.	Pain NRS should be completed daily starting after the Screening Visit. Subjects will complete the diary in the evening (between 5:00 pm and 11:59 pm local time) remotely on their electronic devices. Diary completion should occur every day including on study visit days.
Screening Visit		
5 days after the Screening	Baseline WOMAC and Patient Global Assessment questionnaires (or up until the day before the Day 1 visit)	Complete daily starting on the same day of the Screening Visit (after the visit); pain NRS assessments are to be completed for each knee.
Day 1	N/A	
Week 4 (Day 29)	Complete between Day 26 and 32	Starting on the same day of Day 1 (after the visit), pain NRS assessments are to be completed for the target knee only. Complete daily.
Week 12 (Day 85)	Complete between Day 78 and 92	
Week 24 (Day 169)	Complete between Day 162 and 176	
Week 28 (Day 197)	Complete between Day 190 and 204	

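### SAP 7.1.5 assigns early-termination assessments to visits for FAS analysis, but the protocol plans no WOMAC or Patient Global value at termination

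*SAP*

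**What the plan says.** SAP 7.1.5 states that ET assessments follow the protocol, and then: "If these assessments occur during a scheduled visit, they will be associated with that visit", for FAS analysis. SAP 7.1 gives the FAS its role: "efficacy analyses will be performed on the FAS and PPAS; general safety analyses will be performed on the SAS". A rule written for the FAS is thus most naturally read as a rule about efficacy data.

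Protocol 7.3.6 introduces the ET visit with "If possible, the following procedures and assessments should be performed within 14 days of subject premature withdrawal or termination". Its list covers adverse events and concomitant therapy, medical history, NSAID/acetaminophen usage, physical and knee examination, weight, vital signs and laboratory samples. It names no WOMAC, Patient Global or diary item.

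Protocol 4.1 places WOMAC and Patient Global at baseline and Weeks 4, 12, 24 and 28 only. The questionnaire table in 7.3.8 gives a window for each post-baseline time (for Week 12, "Complete between Day 78 and 92") and has no ET row. Entry is remote and in the evening. Protocol 7.1.1 adds that "electronic diary devices are to be returned to the site at Week 28 (EOS)/ET".

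**The concern.** The SAP has a rule for using ET data in the FAS, but the protocol supplies almost no efficacy data for it. The one efficacy item taken at ET is NSAID/acetaminophen usage, and SAP 12.3 sets the Total NSAID Score to missing for the 28-day period in which a subject terminates.

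WOMAC Function and Patient Global carry hypotheses 2, 4, 5 and 6 in SAP 9. WOMAC Function at Week 12 comes second in the fixed sequence, so every later test depends on it. Protocol 5.6.1 lists lack of efficacy among the reasons for discontinuation, so a subject's state on leaving may bear on why the later values are missing. The main model assumes missing at random. The multiple imputation in SAP 7.1.6 adjusts for the outcome's baseline and imputes each timepoint independently, so as written it does not use even an observed Week 4 value when imputing Week 12.

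**Working it through.** **Is the gap real?** The visit list in 7.3.6 does not settle it alone. The Week 28 list in 7.3.5 also omits both questionnaires, although they are due then at home. The stronger evidence is the missing ET row in 7.3.8 together with the timepoints in 4.1. Return of the device at ET then ends any later entry.

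**The plan's own figures.** SAP 5 re-estimates about 500 subjects, with 225 evaluable per arm after 10% dropout: 2 × 225 / 0.9 = 500, as stated.

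WOMAC Function power, with difference 7.5, SD 25, correlation 0.25 and two-sided α = 0.05:
- Residual SD = 25 × √(1 − 0.25²) = 24.21
- Standard error = 24.21 × √(2/225) = 2.28
- Power = Φ(7.5/2.28 − 1.96) ≈ 90.8% without rounding the standard error. A simulation of the baseline-adjusted ANCOVA gives 90.2%; the SAP states 89.8%. The figure is reproduced.

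**How many subjects are involved.** The documents give no dropout timing. Assume 50 dropouts (10% of 500) spread evenly over Days 1–197, with the ET visit on the day of leaving.

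| Day of leaving | Days | Expected number (50 × days/197) |
|---|---|---|
| 1–25: before the Week 4 window | 25 | 6.3 |
| 26–77: Week 4 window up to the Week 12 window | 52 | 13.2 |
| 78–92: Week 12 window | 15 | 3.8 |
| 93–161: between the two windows | 69 | 17.5 |
| 162–176: Week 24 window | 15 | 3.8 |
| 177–197: after the Week 24 window | 21 | 5.3 |

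Inside a Week 12 or Week 24 window: 30/197 = 15%, or 7.6 subjects. That is about 8 in all and about 4 per arm; for either timepoint alone it is about 2 per arm.

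This is an upper bound on values gained. A subject leaving inside a window may already have completed that window's questionnaire at home, and SAP 7.3.2 and 7.3.3 use only the first assessment in a window. An ET visit is also held only where possible.

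**What recovery would do to power.** The same formula for WOMAC Function gives:
- 225 per arm: 90.8%
- 227 per arm: 91.0%
- 229 per arm: 91.2%. This credits both windows to one timepoint, so it is generous.

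**Values outside a window.** The other 42 or so dropouts would leave outside both windows. Under the current SAP an ET value from them would add nothing to the Week 12 or Week 24 analysis. The mapping rule would not place it at either visit, and the imputation model takes only baseline as a predictor.

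**The case against.** The case against runs as follows.

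- SAP 7.1.5 promises no WOMAC at ET. It applies only when ET assessments coincide with a scheduled visit, and such a subject may already have completed the questionnaire at home. A subject who leaves shortly before a window could also still hold the device when it opens, because the ET visit may follow up to 14 days later. All this stands, and it is why 8 is a ceiling. Completion beforehand is still not assured: entry is confined to the evening, and a subject who hands in the device early in a window cannot complete it that night.
- The sample size already counts dropouts as non-evaluable, so no planned power is lost. This stands.
- SAP 7.1.6.1 tests departures from missing at random for WOMAC and Patient Global. That is a partial answer. It runs only where the imputed result is significant, and it shifts imputed values without adding any information on the state of those who left.
- SAP Appendix 1 (visit windows) was not available for this review and may contain an ET rule. Such a rule could clarify the mapping but could not supply data the protocol does not collect.
- The SAP is written in the past tense and signed in October 2021, so a protocol change probably comes too late for this trial. This largely stands.

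A reader might go further and infer that dropouts leave no usable WOMAC or Patient Global data, or that the primary analysis is compromised. Neither follows. SAP 9.3.1 keeps all timepoints in the MMRM, so a subject who completed Week 4 and left in Week 11 still contributes that value. Pain NRS is recorded daily at home and averaged by study day whatever the visit dates (SAP 7.3.1).

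**Conclusion.** The point holds as a small gap between the two documents. The SAP provides for ET data in the FAS analysis, while the protocol plans no WOMAC or Patient Global value at termination. It concerns secondary endpoints only, though these make up four of the six hypotheses in the sequence.

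If 50 dropouts are spread evenly, at most about 8 subjects are in a position to add a Week 12 or Week 24 value, worth less than half a percentage point of power. Clustered dropout would change that count. Nothing in the documents shows that the treatment estimate is biased, and this point does not claim so. The gain is knowledge of how subjects stood when they withdrew, which would support the missing-data assumption or cast doubt on it. For ET values outside a window, that gain depends on changing the imputation model as well. This is a cheap improvement, not a defect that threatens the trial's conclusions.

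**What to change.** **Protocol.** Add WOMAC and Patient Global, completed on the device before it is returned, to 7.3.6 and to the tables in 7.3.7 and 7.3.8. Allow an exception to evening-only entry for these ET questionnaires.

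**SAP.** In 7.1.5, say which data the rule covers. Keep the in-window mapping together with the first-in-window rule. In 7.1.6, replace the baseline-only, timepoint-by-timepoint imputation with a model that also uses earlier post-baseline values and any ET value as predictors. Using the earlier post-baseline values needs no new data collection, so that part does not depend on the protocol change.

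**Cost.** A minor amendment, a few minutes per withdrawing subject on a device already issued, some daytime entries where all others are made in the evening, and a revised imputation specification. The protocol part helps only subjects who withdraw after the amendment. If follow-up here is complete, it serves a later protocol and only the SAP changes remain relevant to this trial.
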